**Aim 2 – Study Visit 1:** During Study Visit 1, participants will complete a baseline self-report questionnaire, and the study team will conduct a short training around operation of the digital pill system (i.e., digital pills, Reader device, and mobile application) and instruct participants on basic troubleshooting of the technology. We will also help participants to download the mobile application where their adherence data will be recorded and accessible, train them on how to use the app, and register them on the collaborator interfaces (iAssist and Nomi). Participants will be provided with a 30-day supply of digital PrEP (Truvada); participants will then ingest their first digital PrEP dose during the visit to demonstrate their understanding of how to operate the digital pill system and to ensure the technology is functioning properly. Participants will receive a brief reference guide (see *refguide*) with key contact information and basic information regarding the digital pill and Reader. Participants will be scheduled for Study Visit 2, which will occur a maximum of 30 days (i.e., 23-30 days) after Study Visit 1, in order to ensure that participants do not run out of digital pills prior to receiving a refill. We will contact study participants via text message on days 1, 2, 5, and 7 to ensure technology is functioning. Additionally, beginning one week after Study Visit 1, participants will receive brief weekly surveys through the Nomi interface asking them to self-report substance use and sexual activity (see *DigiPrEP Study Messages\_Participant Only*). At the end of Study Visit 1, participants will be remunerated via a \$25 check.

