**Aim 2 – Study Visit 2:** We will contact participants on days 23, 25, and 29 to remind participants of their Study Visit 2 appointment. During this study visit, participants will have blood drawn via phlebotomy and placed on a blood spot card in order to assess PrEP adherence. De-identified specimens will be banked for future use in drug abuse screening. We will review digital pill adherence data with participants in Nomi and conduct a pill count to validate adherence data from the digital pill and Reader. We will review discordant counts, periods of Reader activity that suggest no use of the Reader device, and digital pill use with the participant. We will additionally review any potential nonadherent events detected by the digital pill with participants using timeline followback to gauge potential reasons for nonadherence. We will view the adherence interface with study participants and discuss events surrounding potential nonadherence events. We will record user responses to

each of these timeline followback events. We will also dispense an additional 30-day supply of digital pills to participants. We will schedule participants for Study Visit 3 prior to discharge, which will occur a maximum of 30 days (i.e., 23-30 days) after Study Visit 2. Participants will be reminded that we will pass their adherence data along to their PCP; participants will have the option of opting out of this mechanism at each study visit. At the end of Study Visit 2, the participant will be remunerated via a \$25 check.

**Aim 2 – Study Visit 3:** We will contact participants on days 53, 55, and 59 to remind them of their Study Visit 3 appointment. During this visit, we will review adherence data from the digital pill in Nomi, conduct pill counts with participants, address discordant counts and review reader activity with the participants and address any nonadherence events potentially linked to sexual activity or substance use. The participant will receive a final 30 day refill of digital pills and will be remunerated via a \$50 check.

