**Aims 2/3 – Study Visit 4:** This is the final study visit. We will contact participants on days 83, 85 and 89 to remind participants of Study Visit 4, including a reminder to bring all DigiPrEP equipment to this visit to return to the study team. Participants will have blood drawn for adherence, and we will review adherence data from the digital pill in Nomi and conduct pill counts. Additionally, we will conduct a 20-minute semi-structured interview (see *Aim 3 Exit Interview*) to assess participants' experience working with DigiPrEP and participating in the study. Participants will be encouraged to return to their PCP for continued PrEP prescribing. If they do not have a provider who can continue to prescribe PrEP following the end of the study, we will refer them to a provider at Fenway Health or the Brigham and Women's Hospital infectious disease clinic. Participants will be remunerated a total of \$150 at the end of this visit (i.e., the planned \$75, as well as an additional \$75 for assistance finding and troubleshooting bugs in the mobile app, and for completion of all study procedures).

Participant contact: We will contact participants via text message at described times after study visits (see *DigiPrEP Study Messages\_Participant Only*). Additionally, if participants do not respond to text messages (e.g., technology check-ins at days 1, 2, 5, 7), or to study appointment reminders, we will contact them via phone, text, and/or email. If we do not detect digital pill ingestions for 48 hours (2 doses) or if there are more than 2 missed doses in a week, we will contact participants via phone, text, and/or email to understand if there are issues with operating the digital pill or if missed doses represent true medication nonadherence. If we are unable to reach participants, we will leave phone or text messages, and call participants back the next business day. We will also communicate information about the study, including required lab work documentation for the Screening Visit, to participants via email.

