Drug procurement: Digital pills are procured from Curant Pharmacy (our collaborating pharmacy). Once participants sign informed consent during the Screening Visit, and we have confirmed qualifying laboratory work and eligibility, we will securely email a Drug Order Form to Curant. This order form will contain the following information, as required by Curant: (1) participant's name; (2) participant's date of birth; (3) participant study ID number; (4) participant's anticipated start date; (5) target drug delivery date; and (6) delivery information for pharmacist at Fenway Pharmacy. Following receipt of the Drug Order Form, Curant will FedEx 90 digital pills (three 30-day supplies) to the Fenway Pharmacy. Confirmation of shipment receipt will be documented in the DigiPrEP Pharmacy SOP binder. At Study Visits 1, 2, and 3, we will complete a Prescription Card that study staff will bring to the Fenway Pharmacy, who will sign out drug to us. If participants no-show during their study visit, we will return and sign back in drug to the Fenway Pharmacy. In the event that a participant drops out of the study and we have remaining drug assigned to them in the Fenway Pharmacy, we will securely email a Cancel Order Form to Curant, along with a new Drug Order Form, requesting the required number of replacement bottles of drug, and/or new participant labels (as applicable). Curant will mail new participant labels to place on existing bottles of drug, as well as any additional bottles of drug, as needed.

Study visit scheduling: We will schedule study visits as close to 30 days apart as possible. Recognizing that participants may have scheduling conflicts, we will seek to schedule participants for study visits 2, 3 and 4 within 7 days prior to the 30-day mark in order to prevent participants from running out of digital PrEP pills.

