### **Study Visit 2: Day 30 (-7 days)**

- Review DigiPrEP data
- Blood draw for adherence
- Refill 30 days of PrEP (Truvada digital pill)

- DigiPrEP interface text messages on days 53, 55, 59 to remind participants of Study Visit 3

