DigiPrEP Statistical Analysis Plan

Official title: Feasibility and Acceptability of Digital Pills to Monitor PrEP Adherence in MSM With Substance Use

NCT number: NCT03842436

Document date: September 03, 2021

DigiPrEP Statistical Analysis Plan

Sociodemographics.

Descriptive statistics were calculated for selected variables.

Digital pill system (DPS) performance and engagement metrics.

To analyze the performance of the DPS, the ground truth of PrEP ingestion events were defined as the pill counts obtained each month (i.e., the number of unused pills returned, subtracted from the number of pills previously dispensed). The number of DPS-recorded ingestions – which included the number of both Reader-detected and manually-reported ingestions – was compared with the aggregate pill count at each monthly timepoint; this was defined as the overall performance metric for the DPS. The Reader-detected ingestions count was used to reflect the number of times the DPS was operated correctly. Successful DPS operation was defined as ingestion of a digital pill, proper use of the wearable Reader, and confirmation of the ingestion on both the Reader and the app.

Reader-detected ingestions and manually-reported ingestions that co-occurred within 30 minutes were identified and reconciled; these events likely represented episodes in which a digital pill was ingested, and the ingestion was detected by the Reader, but the participant elected to manually record the ingestion in-app because the Reader was not correctly paired to the smartphone or was delayed in detecting the ingestion. Additionally, several ingestions were manually reported due to a known programming error in the app early in the study. As such, two participants were instructed to manually log all ingestions until an app update was made available; ingestion data for these two individuals were downloaded from their Readers at the end of the study period, and all Reader-detected ingestions were reconciled with manually-reported ingestions.

Participant engagement with the DPS was measured by calculating the total number of DPS-recorded ingestions and comparing the number of monthly DPS-recorded ingestions across each month of the study period.

TFV-DP in DBS.

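### Engagement is measured by raw ingestion counts with no days-observed denominator and no definition of a month, so the counts mix engagement with observation time

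*SAP*

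**What the plan says.** **SAP, DPS performance and engagement metrics.** Engagement is a total count of DPS-recorded ingestions, together with "comparing the number of monthly DPS-recorded ingestions across each month of the study period". The section gives no denominator in days, no definition of a month, and no rule for early visits, late visits or dropout. The nearest hint is in the separate performance metric, where the DPS count "was compared with the aggregate pill count at each monthly timepoint". That suggests visit intervals but does not define them for engagement.

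**Protocol V, Study Procedures.** Visit 2 is one "which will occur a maximum of 30 days (i.e., 23-30 days) after Study Visit 1", and Visit 3 one "which will occur a maximum of 30 days (i.e., 23-30 days) after Study Visit 2". The scheduling paragraph places Visits 2, 3 and 4 "within 7 days prior to the 30-day mark" and adds: "We will schedule study visits as close to 30 days apart as possible". The flow chart instead anchors the three visits to days 30, 60 and 90, each with an allowance of 7 days early. Before Visit 4 participants are reminded to "bring all DigiPrEP equipment to this visit to return to the study team", so observation stops there. The drug procurement paragraph foresees dropout.

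**SAP, TFV-DP in DBS.** Some blood-spot samples were excluded because scheduling problems put them more than five days after DPS recording had ended. The samples that were kept are compared with an average over the preceding three weeks, which is a time-standardised quantity. Engagement has no equivalent.

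**The concern.** With one dose a day, the expected number of recorded ingestions is the daily recording rate multiplied by the days observed. A raw count therefore moves when either factor moves, and the stated metric cannot tell them apart. The monthly comparison is the SAP's only stated measure of engagement over time in a feasibility study of this technology. The risk is that a rise or fall in monthly counts is read as growing or fading engagement when it reflects interval length or a participant leaving. No test, threshold or decision depends on the metric, so what is at stake is how a descriptive result is read.

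**Working it through.** The plan gives no engagement figure to reproduce, and no actual visit dates. The figures below are illustrations under stated timing assumptions, with constant daily engagement.

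**Inputs.** N = 15 (protocol II, Aim 2). Intervals of 23-30 days, and visits on days 23-30, 53-60 and 83-90 (protocol V). Visit 1 is day 0. Let d1, d2, d3 be the days by which each interval falls short of 30. Both sets of windows are met when each d is a whole number of at least 0 and d1 + d2 + d3 ≤ 7. That gives C(10,3) = 120 schedules, out of 8 × 8 × 8 = 512 that meet the flow-chart windows alone.

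**1. One participant.** Visits on days 23, 53 and 83 give intervals of 23, 30 and 30 days: 30/23 = 1.304, or +30%. Visits on days 30, 53 and 83 give 30, 23 and 30 days: 23/30 = 0.767, or -23%. Both schedules meet both sets of windows. A constant daily recording rate cancels from these ratios.

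**2. Mean of 15, exchangeable intervals.** If all 120 schedules are equally likely, each d averages 7/4 = 1.75, so each interval averages 28.25 days and the built-in shift is 0%. The variance of each d is 2.8875 and the covariance is -0.9625, so a difference between two intervals has variance 2 × (2.8875 + 0.9625) = 7.70. The SE of the month-to-month change in the mean is √(7.70/15) = 0.716 days, or 0.716/28.25 = 2.5%. The 95% range is 1.96 × 2.5% ≈ ±5%. This is the range of the *change*; a single month's mean has a half-width of about 3.0%.

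If visits fall only in the last three days of each window (d1 + d2 + d3 ≤ 2, 10 schedules), intervals average 29.5 days. The variance of a difference is 2 × (0.45 + 0.15) = 1.2, and the range is 1.96 × √(1.2/15)/29.5 ≈ ±1.9%.

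**3. Mean of 15, each visit uniform in its remaining window.** Both sets of windows are still met. The mean of d1 is 3.5, of d2 (7 - 3.5)/2 = 1.75, and of d3 (7 - 5.25)/2 = 0.875. Intervals average 26.5, 28.25 and 29.125 days. Month 3 against month 1 is 29.125/26.5 = 1.099, or +9.9%, with no change in behaviour. The SE of that difference is 0.797 days, so the shift is 2.6 ± 1.6 days.

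**4. If a month were a fixed 30-day block.** The third block is cut short at Visit 4. With Visit 4 on days 83-90, the shortfall is 0/30 to 7/30, or 0-23.3%.

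| Timing, both windows met | Mean intervals (days) | Shift, month 1 to 3 | Fixed third block short by |
|---|---|---|---|
| Last three days of each window | 29.5 / 29.5 / 29.5 | 0% | 1.5/30 = 5.0% |
| All 120 equally likely | 28.25 / 28.25 / 28.25 | 0% | 5.25/30 = 17.5% |
| Uniform in remaining window | 26.5 / 28.25 / 29.125 | +9.9% | 6.125/30 = 20.4% |

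**5. Totals.** Visit 4 on day 83 rather than day 90 lowers a participant's total by 7/90 = 7.8%. One of 15 lost before month 3 lowers that month's group total by 1/15 = 6.7%, if participants contribute equally.

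**The case against.** The best defence is that a month plainly means the visit interval. Pills are dispensed and counted at visits, and nothing in the documents describes calendar blocks. The protocol also aims for spacing close to 30 days, which would keep the artefact small. The study is a pilot of 15, not powered for degree of adherence, and the metric is descriptive. Most of this stands: the visit interval is the likelier reading, the fixed-block figures are secondary, and the consequence is limited. It does not remove the point, because intervals of 23 to 30 days still move individual and mean counts on that reading.

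A reader might infer more than the documents support:

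- *A shift of about 13%.* The flow-chart windows alone, with uniform timing, give intervals of 26.5, 30 and 30 days (30/26.5 = 1.132). But in 28 of 64 combinations (44%) the second interval then exceeds the 30-day maximum set in the visit descriptions.
- *A third block up to 70% short.* Three 23-day intervals put Visit 4 on day 69 (21/30 = 70%). That lies outside the flow chart's days 83-90.
- *Proof that visits ran out of window.* The excluded blood-spot samples show that recording ended before sampling in some cases. They do not show that a visit was late.
- *The performance metric is equally affected.* It is not, because the DPS count and the pill count cover the same interval.

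In the other direction, meeting the windows does not guarantee zero shift. That result needs exchangeable intervals, which the documents do not state.

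**Conclusion.** The point stands as a modest one that should be acted on. The SAP's engagement counts depend on days observed, and nothing in the plan separates the two. Within the protocol's windows an individual's monthly count can change by -23% or +30% with unchanged behaviour. The shift in the mean of 15 cannot be fixed from the documents. It is 0% on average under exchangeable intervals, with about ±5% chance variation if all 120 schedules are equally likely and less if visits cluster near 30 days. It is about +10% from month 1 to month 3 under uniform placement in the remaining window. On the less likely fixed-block reading, the third block is 0-23% short. Dropout adds to any of these. All figures assume constant daily engagement and visits inside the windows; late visits are not modelled. No hypothesis test or decision rule is affected.

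**What to change.** Add a few sentences to the SAP's engagement section:

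- Define a month as the visit interval.
- For each participant and month, report DPS-recorded ingestions divided by days observed. Compare months descriptively, within participant, on that rate.
- Show total counts only beside person-days.
- Count days from one visit to the next, or to dropout. Tabulate separately the days after dispensed pills could have run out and the days after DPS recording ended, and show the rate with and without them. Both versions are needed: keeping those days counts a lack of pills or equipment as disengagement, and removing them could hide participants who simply stopped using the system.

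No model is needed. Ingestions are date- and time-stamped (protocol IX, Data Tracking), pill counts are taken at Visits 2, 3 and 4, and the SAP uses blood-spot collection dates at months one and three. The Visit 3 date is assumed to be in the visit record. The cost is one re-tabulation, and the only real effort is agreeing the day-count rule.

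As a separate point, the visit-by-visit windows, the scheduling paragraph and the flow chart in protocol V must be reconciled. They can all be met together, but a schedule can satisfy one description and break another.

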Participant messaging: Participants will receive standard SMS text messages, as well as notifications from the mobile application which receives their adherence data from the digital pill. Upon enrollment in Nomi and iAssist interfaces at Study Visit 1, participants will receive a welcome message, including a contact number for the DigiPrEP study team. Participants will receive three technology check-in messages during the first week using the digital pill (on days 2, 5, and 7); these messages will prompt participants to respond with “0” for “I need help with something,” or “1” for “Everything’s OK!” If participants text back “0,” the study team will contact the participant to assist them further. Beginning one week after Study Visit 1, participant will also receive an anonymous REDCap link to a brief weekly survey, asking them to self-report substance use and sexual activity for the past week. Participants will also receive text messages reminding them of upcoming study visits. Depending on messaging settings in the Nomi interface, participants may also receive app notifications for ingestion confirmations, as well as messages related to Reader battery life and confirmations of manually recorded ingestions (see *DigiPrEP Study Messages\_Participant Only* for detailed content and timing of all participant messaging).

Potential participant directly contacted study RA, referred by Fenway Health primary care physician, or identified via medical record review and screened during clinical appointment at Fenway Health

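### Engagement is compared on raw monthly counts although the months differ in length (23-30 days) and only month one contains a staff-observed training dose

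*SAP*

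**What the plan says.** The SAP, under digital pill system (DPS) performance and engagement metrics, measures engagement by the total number of recorded ingestions and by "comparing the number of monthly DPS-recorded ingestions across each month of the study period". A recorded ingestion is broadly defined: the count is one "which included the number of both Reader-detected and manually-reported ingestions". The Reader-detected part is read as the number of times the system was used correctly. No per-day or per-pill denominator is given for the engagement comparison, and no day or dose is set aside.

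The protocol (section V, Study Procedures) fixes the conditions of each month:

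- **Observed dose.** At Study Visit 1, after training, "participants will then ingest their first digital PrEP dose during the visit to demonstrate their understanding of how to operate the digital pill system". No ingestion is scheduled at Visits 2, 3 or 4.
- **Interval.** Visit 2 falls 23-30 days after Visit 1, and Visit 3 falls 23-30 days after Visit 2. The scheduling paragraph gives Visit 4 the same seven-day window.
- **Check-ins.** "We will contact study participants via text message on days 1, 2, 5, and 7 to ensure technology is functioning". The participant messaging paragraph lists only days 2, 5 and 7. The two lists should be reconciled, but both lie in the first week.
- **Later support.** At Visit 2, "We will review digital pill adherence data with participants in Nomi and conduct a pill count", and Visit 3 repeats the review. Contact after 48 hours without a detected ingestion, or after more than two missed doses in a week, has no stated month limit.

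**The concern.** A monthly count has a meaning across months only if each month offers the same opportunity to record an ingestion under similar conditions. Here neither holds. A participant seen at day 23 has seven fewer days on which to record a dose than one seen at day 30. Month one alone includes a dose taken in front of staff as part of training.

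The observed dose also raises a question of meaning. If the Reader detects it, it enters the count that the SAP reads as correct operation, so someone who never used the system at home would still be credited with one. At stake is how a reader interprets a rise or fall between months, and what the month-one performance figure says about independent use.

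**Working it through.** The plan states no figure for this comparison, so there is none to reproduce.

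**Inputs from the documents.** Interval n = 23 to 30 days; one observed dose per participant, in month one only; N = 15 (Specific Aims, Aim 2).

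**Assumptions.** p is the probability that a home dose is recorded on a given day. The documents do not give it; I use 0.6 to 0.9, with 0.8 as the central value. A month is taken as the interval between visits, as for the pill counts, because the SAP does not define it for engagement. The observed dose is taken as certain to be recorded, which makes its effect an upper bound.

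**1. Interval length.** Difference in expected count between a 30-day and a 23-day month = 7p.

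- p = 0.6: 4.2; p = 0.8: 5.6; p = 0.9: 6.3 ingestions per participant.
- Relative to the 30-day count: 7p / 30p = 23.3% at any p.

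Either month may be the short one, so the sign can go either way. For the group as a whole, the full 23% arises only if every participant's visits sit at opposite ends of the window.

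**2. Observed dose.** Month-one rate = (1 + p(n − 1)) / n, so the excess over p is (1 − p) / n.

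| p | n = 23 | n = 30 | Extra ingestions per participant (1 − p) |
|---|---|---|---|
| 0.6 | +1.7 points | +1.3 points | 0.4 |
| 0.8 | +0.9 points | +0.7 points | 0.2 |
| 0.9 | +0.4 points | +0.3 points | 0.1 |

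At p = 0.8 the group excess is 15 × 0.2 = 3 ingestions, out of at most 15 × 30 = 450.

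**3. Both together, with constant home use at p = 0.8.**

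- Month one 30 days, month two 23 days: 1 + 29 × 0.8 = 24.2 against 23 × 0.8 = 18.4, an apparent fall of 5.8.
- Month one 23 days, month two 30 days: 1 + 22 × 0.8 = 18.6 against 30 × 0.8 = 24.0, an apparent rise of 5.4.
- With the observed dose removed and home days as denominator: 17.6/22 or 23.2/29 in month one, and 18.4/23 or 24/30 in month two. All equal 0.80.

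**4. First week.** If every dose on days 1-7, counting the observed dose as day 1, were recorded, the excess would be 7(1 − p): 1.4 ingestions at p = 0.8, or 1.4/24 = 5.8% of a 30-day count. This is a ceiling. The documents give no estimate of what the check-ins do.

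**5. Dropout.** If the comparison uses group totals, losing one of 15 participants lowers a later month by 1/15 = 6.7%.

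**The case against.** A reader might infer that a decline from month one is built into the comparison, since the observed dose and all scheduled technology check-ins fall there. The documents do not support that. The observed dose contributes only 1 − p, under one point at p = 0.8. The check-in messages ask whether help is needed; they are not dose reminders, and any lift from them is an assumption. If they did increase use, the ingestions would be real, and a later fall would be a real change in engagement. Other features could favour later months: the individual adherence reviews at Visits 2 and 3, missed-dose contact without a month limit, the learning period in month one, and the app error that the SAP reports early in the study. The last is softened because manual reports count and Reader data were reconciled. The net direction cannot be fixed.

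It can also be said that a proof-of-concept study may properly measure the system as deployed, onboarding included, and that the observed dose shows the participant's own understanding. This is a fair argument against dropping the first week from the main comparison. It is weaker for a dose taken under observation in training, which says little about use at home.

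Finally, the protocol aims for visits as close to 30 days apart as possible, so typical intervals may differ by less than seven days. The comparison has no stated test, threshold or decision rule, and the protocol's Biostatistical Analysis section disclaims power to determine the pill's effect on adherence. Both points limit the consequence. Neither supplies the missing denominator.

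**Conclusion.** The concern holds as a question of comparability, not as a demonstrated bias towards decline. The larger part is the missing denominator: up to 23% of a 30-day count, of either sign, or 5.6 ingestions per participant at an assumed 80% recording rate. This rests on months being the intervals between visits, and it is the extreme of the permitted window. The smaller part is the observed dose: 0.3 to 1.7 points on the month-one rate for assumed home recording rates of 60-90%, upward only, plus one credited operation that does not show independent use. The effect is on the interpretation of descriptive figures, so this is a minor improvement to the plan.

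**What to change.** In the SAP:

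1. Compare months on recorded ingestions per observed day. Define observed days as days in the study with digital pills dispensed, not days of Reader activity; otherwise disengaged days would leave the denominator.
2. Exclude the Visit 1 observed dose from the Reader-detected count, the DPS-recorded count and the month-one pill count, so that numerator and reference stay matched. Start month one on the following day.
3. Report set-up success at Visit 1 as its own figure (n of 15).
4. Add a sensitivity row that omits days 1-7. Keep this out of the main comparison, where it would be a debatable choice of what to estimate.
5. State that a month-to-month change is not purely a change in engagement, and name the features that differ between months.

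The cost is SAP wording and a re-tabulation. The protocol's data tracking paragraph says records carry a date and time stamp, and the SAP already matches Reader and manual entries within 30 minutes, so no new data are needed. The downside is one dose fewer per participant and a slightly less favourable month-one figure.

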### **Study Visit 4: Day 90 (-7 days)**

- Review DigiPrEP data, pill counts, return equipment
- Blood draw for adherence

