We also compared drug concentrations of TFV-DP as measured in DBS at months one and three to DPS-recorded PrEP adherence. First, we identified all DBS samples that, as a result of scheduling challenges, were obtained more than five days after the conclusion of DPS-recorded ingestions, and excluded these DBS samples from analysis, as they resulted in incomplete data to compare with DPS-recorded ingestions. All other DBS samples were paired, based on their collection dates, with the corresponding average of DPS-detected ingestions during the three-week period prior to DBS collection. We dichotomized TFV-DP levels using a cutoff of ≥ 700 fmol/punch to indicate at least four doses of PrEP ingested per week.^{1,2} Using TFV-DP in DBS < 700 vs ≥ 700 fmol/punch as a dichotomous variable, and considering the granular continuous adherence data from the digital pill, we then calculated a point biserial correlation between TFV-DP in DBS and digital pill adherence. Finally, we analyzed the paired TFV-DP concentrations and DPS-recorded adherence data at months one and three, and calculated Pearson's correlation coefficients for each independent timepoint. Analyses were completed using SAS (version 9.4).³

Qualitative analyses.

Qualitative user experience interviews were transcribed and coded using applied thematic analysis.^{4,5} A codebook was generated. All interviews will then double-coded by two study team members; coding was paused and evaluated every five transcripts to ensure consistency and to resolve and document any discrepancies. A kappa statistic was calculated, utilizing a cutoff of > 0.8 to ensure interrater reliability between coders. Coders reviewed aggregate coding to identify and discuss final

themes surrounding user experiences, which were reviewed by the study team as a whole. Qualitative analyses were facilitated by NVivo software.⁶

References

3. SAS Institute Inc. *SAS.*; 2013.

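### The SAP compares raw monthly ingestion counts although visits may be 23 to 30 days apart; ingestions per observed day should be reported beside them

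*SAP*

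**What the plan says.** In the SAP's section on DPS performance and engagement metrics, engagement is the total number of DPS-recorded ingestions together with "comparing the number of monthly DPS-recorded ingestions across each month of the study period". No rate or denominator is given. The section takes its pill counts each month and speaks of monthly timepoints. In the protocol these are the study visits, but the SAP does not state the length of a month in days.

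The protocol (V. Study Procedures) makes the interval variable. Study Visit 2 is one "which will occur a maximum of 30 days (i.e., 23-30 days) after Study Visit 1", and Study Visit 3 is one "which will occur a maximum of 30 days (i.e., 23-30 days) after Study Visit 2". The paragraph on visit scheduling sets the aim: "We will schedule study visits as close to 30 days apart as possible". It then allows Visits 2, 3 and 4 to be booked "within 7 days prior to the 30-day mark" when participants have scheduling conflicts. The flowchart places Visits 2, 3 and 4 at Day 30, 60 and 90, each with a window of minus 7 days. Its entry for Visit 4 reads "Review DigiPrEP data, pill counts, return equipment", so recording ends then at the latest. Dosing is once daily.

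**The concern.** The month-by-month comparison is there to show whether participants keep using the system. A count serves that purpose only if every month offers the same number of days on which a dose could be recorded. The protocol allows months of different length, so a difference in counts mixes engagement with scheduling. A short interval can look like a drop in use. A short interval followed by a full one can hide a real drop. In a small pilot whose output is descriptive, a reader has only the reported figures and no way to separate the two.

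**Working it through.** The documents give no figure of their own to reproduce here, so this is direct arithmetic from the visit rules.

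**Inputs.** One dose per day (Protocol V). Interval between consecutive visits 23 to 30 days (Protocol V, Study Visits 1 and 2 and visit scheduling). Flowchart windows: Visit 2 on days 23-30, Visit 3 on days 53-60, Visit 4 on days 83-90. Aim 2 sample size 15 (Protocol II).

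**Step 1: largest difference between two months.** Expected count = adherence × days, so at a common adherence the ratio of two counts is the ratio of their days.
- 23 against 30 days: 1 − 23/30 = 7/30 = 23.3% lower. With the shorter interval as base, 7/23 = 30.4% higher.
- At 100% adherence the counts are 23 and 30; at 80% they are 18.4 and 24. The relative difference is the same.
- Hidden change: 23 doses in 23 days (100%), then 23 doses in 30 days (23/30 = 76.7%), both count as 23.
- Two 30-day intervals: no difference.

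**Step 2: months run visit to visit.** Write each interval as 30 minus a shortfall of 0 to 7 days. There are 8 × 8 × 8 = 512 combinations. The flowchart windows require the three shortfalls to total at most 7, which leaves 120 schedules. Assume that these are equally likely.
- Mean shortfall per interval = 7/4 = 1.75 days, so the mean length is 28.25 days in each of months 1, 2 and 3. There is no drift.
- SD of (interval 3 − interval 1) = 2.77 days.
- Standard error of the mean difference for 15 participants = 2.77/√15 = 0.72 doses at full daily use, from interval length alone.

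**Step 3: months as fixed 30-day blocks.** Under the flowchart, blocks 1 and 2 are complete and block 3 has (Visit 4 day − 60) days.
- Visit 4 on days 83, 84, …, 90 gives 23, 24, …, 30 days.
- All on day 90: fall of 0%. Spread evenly over days 83-90 (assumption): mean 26.5 days, 1 − 26.5/30 = 11.7%. All on day 83: 23.3%.
- These errors have one sign and do not average out over participants.

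**Step 4: why the definition should be written down.** For a participant who never misses a dose, with visits on days 23, 53 and 83, visit-to-visit counts are 23, 30, 30 and 30-day blocks give 30, 30, 23. The same data show a rise or a fall, and neither is real.

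**Step 5: with a denominator.** In Step 1, the rate is 23/23 = 1.00 against 30/30 = 1.00 at equal adherence. In the hidden-change example it is 1.00 against 23/30 = 0.77. The false difference goes and the real one shows.

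**The case against.** The strongest reply is that little depends on this. The protocol aims for 30 days, where the effect is zero, and offers the 7 days only as an allowance. No document shows that an early visit took place. The comparison has no test, threshold or decision attached, and the protocol (VI. Biostatistical Analysis) says that the study is an unpowered pilot. All of this stands, and it limits the point to a small improvement. It does not make a raw count the right summary when the plan itself permits unequal months.

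Four stronger readings are tempting, and the documents do not support them.
- A reader might take 23% as the typical error. It needs one interval at the minimum and another at the maximum.
- A reader might infer a built-in false decline in engagement. That needs fixed 30-day blocks, which the SAP never mentions; its monthly timepoints point to visit-to-visit months.
- A reader might see proof of irregular intervals in the SAP's exclusion of DBS samples that, "as a result of scheduling challenges, were obtained more than five days after the conclusion of DPS-recorded ingestions". That describes samples taken late relative to recording, not early visits. It does show that a plain per-day rate could mislead if days without pills or without recording were counted, and the fix allows for this.
- A reader might extend the problem to the other analyses. The performance metric sets DPS counts against pill counts at the same monthly timepoints, and the DBS comparison uses an average over a three-week period, so neither depends on visit spacing in this way.

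A reader might also notice that the fixed reminder days can fall after an early visit, or that the protocol text and flowchart anchor Visit 3 differently. These change no result. The first also depends on a message file that is not among the documents, and the second is an exception to the 30-day target. They are not part of this point.

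**Conclusion.** The point holds as a modest one. The SAP's month-to-month engagement comparison uses raw counts over intervals that the protocol lets vary from 23 to 30 days, so it can create or mask a change. The range runs from zero at the 30-day target to 23% at the extreme. On the more natural visit-to-visit reading the effect is extra noise of about 0.7 doses (standard error, month 1 to month 3 mean difference, 15 participants) without drift. That figure rests on full daily use, on equally likely schedules and on both visit rules being kept. A one-way fall of 0 to 23% in month 3 arises only under fixed 30-day blocks. The actual visit dates are not in the documents, so the size in this trial cannot be stated more closely.

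**What to change.** Define month in the SAP as the interval from one study visit to the next. Beside each raw count, report DPS-recorded ingestions divided by days observed in that interval. Leave out of the denominator days after the dispensed pills could have run out, and days after DPS recording had ended for equipment or scheduling reasons. Keep days missed while pills and a working system were available, since those are the non-engagement that the measure should capture.

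The SAP is written in the past tense, but this can still be added, because it needs only visit dates and the time-stamped ingestion records. There are no extra visits, participants or tests. The cost is one more descriptive figure per month and a small judgement, best written down, about which days count.
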